### **7.2. Efficacy variables**

For the primary objective 1, efficacy will be measured by determining Hyfe's capacity to predict a diagnosis, or reflect clinical evolution of patients, based on cough signatures. For this, the acoustic characteristics of coughs (mean frequency, volume, amplitude) registered from participants with an etiologic diagnosis, will be described, to identify patterns associated to specific conditions. Additionally, the Area Under the Curve, sensitivity, and specificity of the AI system will be retrospectively evaluated with the annotated cough registries.

For the secondary objective 1, the efficacy variable will be the daily score in the online VAS, and the coughs per recorded hour.

For the secondary objective 2, there is no clear efficacy variable. We will retrospectively include anonymous coughs registered in patients with an etiologic diagnosis and annotated with data in online datasets from where they can be used to train this and similar AI systems in the future.

For the secondary objectives 3 and 4, efficacy variables will include the calculated sensitivity, specificity, positive predictive value (PPV), and negative predictive value (NPV) of Hyfe, compared to two trained human observers.

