### **7.3. Schedule for evaluation, recording and analysis of the efficacy parameter**

Participant recruitment is set to start in Q3 2021. Cough registries of patients with an etiologic diagnosis will start to be included in the annotated datasets as soon as the diagnosis is reached.

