## 9. STATISTICS

### ***9.1. Description of the statistical methods to be used, including the schedule of all the planned intermediate analyses***

For completion of the primary objective

To assess the accuracy of the cough surveillance system to detect cough patterns associated to specific diseases, we will use participants in which an etiologic diagnose is reached before completion of the study. We will search for digital footprints of singular detected cough events, and/or the pattern of cough in time for participants with a given diagnosis.

These records will be used to train a previously developed convolutional neural network to perform respiratory disease cough classification. We will initially use a random split-sample approach (70% derivation & 30% validation) to assess the performance of the newly generated cough classification tool (sensitivity, specificity, positive and negative predictive values, AUC). Performance will then be validated by retrospectively analyzing these participants' coughs with the newly trained AI-network.

The cough classification tool will be supplemented with patient-specific information to assess the incremental value of cough-based multi-variable prediction.

For secondary objective 1

The daily VAS score of participants will be compared to the cough frequency registered by the cough surveillance system. These data will be used to fit a linear regression model to compare self-reported VAS scores to daily cough frequency and calculate a correlation coefficient ( $r$ ). The

average weekly VAS score and cough frequency on week 1, will be compared to that at study withdrawal using a paired t-test, and represented using before-after plots. P values below 0.05 will be considered significant. A similar approach will be used to compare results of the LCQ at the beginning vs the end of the study. Before-after plots will be constructed to represent these differences. This approach is also expected to provide information on the system's capacity to reflect clinical evolution of participants (Primary objective).

For completion of secondary objective 2

Cough registries of participants with an etiologic diagnosis of respiratory disease will be included in annotated datasets. There are no specific statistical analysis required for completion of this objective.

For completion of secondary objectives 3 and 4

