## **9.2. Sample size calculations**

### *Primary objective*

For the primary objective, sample size calculations are complicated due to the variability of cough frequency between different patients with different conditions. To evaluate the system's capacity to detect and classify coughs based on their etiology, we will create and prospectively

increase a split-sample (derivation / validation) dataset and test performance until it plateaus (see data analysis). Based on previous digital cough diagnostic studies performed by the co-investigators, we anticipate needing 15,500 individual cough data points and 200 cough time series by groups for every individual diagnosis. This number of coughs might be rapidly reached by participants diagnosed with a cause of chronic cough but will likely take substantial time for other acute conditions. Thus, the suggested duration of 5 years.

To evaluate the capacity of the system to reflect changes in cough frequency associated to clinical evolution, sample size calculations are more straightforward and detailed below.

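### The last validation step for the disease classifier does not exclude participants used in training, and the unit of the 70/30 split is not stated

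*Combined protocol and SAP*

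**What the plan says.** For the primary objective, section 9.1 takes the participants who receive an etiologic diagnosis before the study ends. Of their data it says "These records will be used to train a previously developed convolutional neural network" to classify respiratory disease. It continues: "We will initially use a random split-sample approach (70% derivation & 30% validation"), and attaches sensitivity, specificity, PPV, NPV and AUC to that step. The next sentence is "Performance will then be validated by retrospectively analyzing these participants' coughs with the newly trained AI-network".

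Section 7.2, which defines the efficacy variables, says: "Additionally, the Area Under the Curve, sensitivity, and specificity of the AI system will be retrospectively evaluated with the annotated cough registries". It names no held-out subset.

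The dataset grows during the study. Section 7.3 states: "Cough registries of patients with an etiologic diagnosis will start to be included in the annotated datasets as soon as the diagnosis is reached". Section 9.2 plans to "increase a split-sample (derivation / validation) dataset and test performance until it plateaus". On size, section 9.2 says "we anticipate needing 15,500 individual cough data points and 200 cough time series by groups for every individual diagnosis", and adds: "This number of coughs might be rapidly reached by participants diagnosed with a cause of chronic cough". It gives no number of participants. No section says whether the split is by cough, by time series or by participant, and none reserves later participants for the final step.

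**The concern.** There are two separate gaps.

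**The last step.** The only group that *these participants* can refer to in section 9.1 is the diagnosed group whose records train the network. If the network is refitted on all records before this step, the result is entirely apparent performance. If it is not refitted, the result mixes training participants with held-out ones. It is free of this bias only if the 30% part was meant, and the text does not say so.

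**The split unit.** A 70/30 split by participant is a sound internal validation. A split by cough is not, because coughs from one person resemble each other and the same person would appear in derivation and validation. If each person gives one time series, this second gap affects only the single-cough analysis.

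The diagnostic half of the primary objective rests on these figures. With a participant-level split the plan has one sound internal estimate, but the text does not secure it, and the later step adds an optimistic figure under the name of validation. If the split is by cough and the last step is read as written, no single-cough estimate comes from people the network has not seen.

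**Working it through.** **The plan's own figure.** The 15,500 coughs and 200 time series per diagnosis (section 9.2) cannot be reproduced. The section cites earlier studies by the co-investigators and gives no target accuracy, precision, power or within-person correlation. It does give a ratio: 15,500 / 200 = 77.5 coughs per series, or per person if each person gives one series (assumption).

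**How often a cough-level split divides a person.** With m coughs, the probability of falling on both sides of a random 70/30 split is 1 − 0.7^m − 0.3^m.

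- m = 2: 42%
- m = 5: 83%
- m = 10: 97%
- m = 20: 99.9%

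At 77.5 coughs, essentially everyone is on both sides.

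**Effect of re-scoring everyone.** After a participant-level split without refit, pooled accuracy is 0.7 × training accuracy + 0.3 × held-out accuracy. For a classifier at chance on unseen people (0.50), with assumed training accuracy:

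- 0.90: 0.7 × 0.90 + 0.3 × 0.50 = 0.78
- 0.95: 0.7 × 0.95 + 0.3 × 0.50 = 0.815
- 1.00: 0.7 × 1.00 + 0.3 × 0.50 = 0.85

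**Simulation with no disease signal (true AUC 0.50).** Two diagnoses, 200 people each, 78 coughs per person (77.5 rounded), Gaussian features, linear discriminant, 200 runs per setting. The number of features and the share of feature variance due to the person are assumptions. Monte Carlo standard error is at most 0.0024. Entries are mean AUC.

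| Features | Person share | Refitted on all, all re-scored | Participant split, all re-scored | Cough-level split, 30% scored | Held-out participants only |
|---|---|---|---|---|---|
| 10 | 0 | 0.510 | 0.508 | 0.500 | 0.500 |
| 10 | 0.1 | 0.529 | 0.524 | 0.525 | 0.500 |
| 10 | 0.2 | 0.539 | 0.532 | 0.536 | 0.498 |
| 10 | 0.4 | 0.557 | 0.548 | 0.554 | 0.502 |
| 50 | 0 | 0.523 | 0.519 | 0.501 | 0.500 |
| 50 | 0.1 | 0.566 | 0.555 | 0.556 | 0.499 |
| 50 | 0.2 | 0.591 | 0.576 | 0.584 | 0.500 |
| 50 | 0.4 | 0.626 | 0.605 | 0.621 | 0.502 |

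Only the last column stays at the true value throughout. With person share zero, the cough-level split is unbiased, so that leak comes through the person.

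**A different classifier.** A 5-nearest-neighbour rule (20 features, 20 coughs per person, 50 or 100 people per group, 10 repeats, all assumed) gave the same direction. At within-person correlation 0.3, the cough-level split gave AUC 0.60 to 0.65 and re-scoring everyone 0.74 to 0.76. Held-out participants stayed at 0.49 to 0.51 for every correlation tried, from 0 to 0.5. Under this rule a re-scored training cough matches itself, so re-scoring is inflated (0.67) even at correlation zero.

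**Precision.** The 30% part of 15,500 is 4,650 coughs. For an illustrative sensitivity of 0.80:

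- Coughs treated as independent: 1.96 × √(0.16 / 4,650) = 0.0115, about ±1.1 points.
- Within-person correlation 0.1 (assumption): design effect 1 + 76.5 × 0.1 = 8.65, half-width 0.0115 × √8.65 = 0.034.
- Within-person correlation 0.4 (assumption): design effect 1 + 76.5 × 0.4 = 31.6, half-width 0.0115 × √31.6 = 0.065.
- Scored once per person, 30% of 200 = 60 people: 1.96 × √(0.16 / 60) = 0.101.

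**The case against.** The strongest case is that this is an ambiguity and not an error. All five metrics are attached to the 70/30 step, which has a part set aside for validation, and the sentence that follows names no metric and does not claim to replace that estimate. *These participants* may mean the 30%. Analysing retrospectively may mean scoring coughs recorded before the diagnosis was known, because section 4.1 uses the word in that sense for building the annotated datasets. Nothing says that coughs are the split unit. Section 7.2 says what is measured, and partitioning belongs in 9.1. The most serious conclusion needs two unconfirmed readings together. The simulated size also depends on a participant count that the plan does not give: holding about 15,500 coughs per diagnosis, a cough-level split gave AUC from 0.508 (1,000 people per diagnosis, 10 features, person share 0.1) to 0.81 (30 people, 50 features, share 0.4). Finally, the study prescribes no treatment (section 6.1), and the primary objective also has descriptive and clinical-evolution parts.

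Part of this stands. The benign readings are possible, section 7.2 is supporting evidence only, and the simulated values neither bound nor estimate the bias.

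The rest does not remove the problem. The benign readings are nowhere stated. The sequence from an initial split to a later validation presents two steps, and the 30% reading would make the second a repeat of the first. Calling the network previously developed gives no protection, because it is to be trained on these same records.

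**Conclusion.** The concern holds, and the text should be corrected before any performance figure is produced: a partition chosen after results are seen is open to influence from them. Followed as written, section 9.1 presents apparent performance, wholly or in part, as validation, and sections 7.2, 7.3 and 9.2 do not prevent it. The missing split unit leaves the one potentially sound estimate unsecured.

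The direction is clear: scoring people used in training overstates discrimination, and held-out participants do not show this bias. The size cannot be derived from the documents. At 200 people per diagnosis with 78 coughs each and a person share of 0.1 to 0.4, a linear classifier with no signal to find reached AUC 0.524 to 0.626 when training participants were scored, and 0.525 to 0.621 under a cough-level split. The planned classifier is a convolutional network, so these values are not a forecast. The conclusion about the text does not depend on them.

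**What to change.** In section 9.1:

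- Make the 70/30 split by participant, stratified by diagnosis, with all coughs and time series of a person in one partition, and keep each allocation as the dataset grows.
- Report AUC, sensitivity, specificity, PPV and NPV as validation results only for participants not used in training, with confidence intervals from resampling participants.
- Delete the last step or label it apparent performance. If the 30% part was meant, say so.

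In section 7.2, limit the stated AUC, sensitivity and specificity in the same way.

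In section 9.2, report the number of participants per diagnosis beside the cough count, without a new recruitment target. It is also advisable to make the plateau checks within the derivation participants, so that held-out participants are scored once. This changes which data inform the decision to stop enlarging the dataset, and the main correction does not depend on it.

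The cost is wording in three sections and a different split key, with no new patients or procedures. Reported performance will be lower than from re-scoring training participants. Intervals will be wider because people, not coughs, determine them, and diagnoses with few participants will have wide ones.

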## **4. DESIGN OF TRIAL**

### **4.1. Global design**

This is a single center study to be carried out at the two campuses of the Clínica Universidad de Navarra, in the cities of Pamplona, and Madrid, Spain.

For the cough-monitoring process, we will use, an Artificial-Intelligence system (AI) that detects and records explosive putative cough sounds and identifies human cough based on acoustic characteristics (see below).

Potential participants either attending the outpatient clinic or hospitalized with a complaint of cough will be invited by their treating physician, or a member of the research team and included in the study by part of the research team. A researcher will instruct participants on how to install and use Hyfe Cough Tracker in their smartphones. If necessary, the researcher might provide participants with a smartphone configured to exclusively run Hyfe Cough Tracker™. Researchers who enroll participants will also be responsible of obtaining informed consent forms personally.

Once turned on, the app will monitor cough. Participants provided with a study phone will be instructed to run the app continuously and keep the study smartphone close to them for the period of monitoring.

Depending on the objective, participants will either be submitted to diagnostic procedures deemed necessary by their attending physician or will receive the treatment recommended by their attending physicians and will be monitored for a variable period.

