#### **Monitoring period**

The monitoring period will vary for outpatient and inpatient participants. Inpatients will be monitored from the moment of first consultation/admission to the hospital until their discharge. Outpatients will be monitored for an initial period of one month, subject to modification

depending on the characteristics of specific diseases under study, and prior obtention of informed consent.

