#### Secondary objective 1:

We estimate needing 28 participants. This accounts for an anticipated effect size in the outcome (VAS score) of 0.35, with one predictor (cough frequency registered by Hyfe), and accounting for a loss of follow up of 10% of the participants. The significance level is set at 0.05, with a statistical power of 80%.

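### Secondary objective 1 fits one regression and one r to daily VAS and cough data without accounting for repeated days per participant, and no analysis links a person's change in cough to that person's change in VAS or LCQ

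*Combined protocol and SAP*

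**What the plan says.** All references are to the combined protocol and SAP.

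- **Model.** Section 9.1, secondary objective 1: "These data will be used to fit a linear regression model to compare self-reported VAS scores to daily cough frequency", together with one r. It names no participant effect, clustering or per-person summary, and no other section does.
- **Data.** Section 4.1 asks for a VAS every day and an LCQ at recruitment and at the end of monitoring. Outpatients are followed for one month initially. For inpatients, "Inpatients will be monitored from the moment of first consultation/admission to the hospital until their discharge".
- **Change.** In section 9.1, the week 1 averages of VAS and of cough frequency "will be compared to that at study withdrawal using a paired t-test". The LCQ is treated in a similar way, start against end.
- **Sample size.** Section 9.2, secondary objective 1: 28 participants, from an effect size of 0.35, one predictor, significance level 0.05, 80% power and 10% loss to follow-up.
- **Purpose.** Section 7.2 defines efficacy for the primary objective as Hyfe's "capacity to predict a diagnosis, or reflect clinical evolution of patients, based on cough signatures". Section 9.1 expects the secondary objective 1 approach to inform the clinical-evolution part. Section 9.2, under the primary objective, refers the reader to the calculations further down for that same part. The only calculation there that fits is the 28.

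**The concern.** Days from one person tend to resemble each other. If all person-days enter one ordinary regression, the standard error treats them as independent and is too small whenever both measures are correlated within people. The resulting r is also a blend. It can arise because Hyfe follows each patient's course, or only because patients who cough more also score higher. Only the first bears on clinical evolution.

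The paired t-tests do not fill the gap, because each compares a measure with itself over time. Nothing relates a participant's change in cough to the same participant's change in VAS or LCQ. The planned outputs could therefore suggest that Hyfe reflects clinical evolution when it does not, or miss it when it does. No other analysis is stated for that part of the primary objective.

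Because the sections name different units, analysts who each follow the protocol could report different values of r and p.

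**Working it through.** **1. The plan's 28.** Section 9.2 does not name the effect-size metric. Read 0.35 as Cohen's f², with one predictor, two-sided 0.05, noncentral F with λ = f²·n and 1 and n−2 degrees of freedom:

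- n = 24 gives 79.1% power; n = 25 gives 80.9%.
- 25 / 0.9 = 27.8, rounded up to **28**.
- The implied r is √(0.35/1.35) = 0.51.

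Other readings of 0.35 do not give 28 after 10% loss: as r, 66; as R², 19; as a paired standardised difference, 75. The calculation therefore counts one independent row per participant.

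**2. The units side by side.**

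| Section | VAS | Cough |
|---|---|---|
| 4.1 | weekly mean | registered frequency |
| 7.2 | daily score | coughs per recorded hour |
| 9.1 | daily score | daily frequency |
| 9.2 | one row per participant (implied) | one row per participant (implied) |

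With complete entries over a month, 28 people supply about 28 × 30 = 840 daily rows.

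**3. False-positive rate on pooled days.** The documents give no ICC. Assume 25 completers, no true association, the same ICC in both measures and exchangeable days. With m days per person, the variance of the estimate is inflated by D = 1 + (m−1)·ICC². The true size of a nominal 5% test is about 2·[1 − Φ(1.96/√D)].

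Worked example, m = 30 and ICC = 0.3: D = 1 + 29 × 0.09 = 3.61; 1.96/1.90 = 1.03; size about 30%.

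| Assumed ICC | D, 30 days | Size, 30 days | D, 7 days | Size, 7 days |
|---|---|---|---|---|
| 0 | 1.00 | 5% | 1.00 | 5% |
| 0.1 | 1.29 | 8% | 1.06 | 5–6% |
| 0.3 | 3.61 | 30% | 1.54 | 11% |
| 0.5 | 8.25 | 50% | 2.50 | 21% |
| 0.7 | 15.21 | 62% | 3.94 | 33% |

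Simulation agrees with the formula to within about one percentage point. With one row per participant the simulated rate is 4.7% to 5.2%.

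**4. What the pooled r measures.** With equal ICCs, pooled r ≈ ICC·r(between) + (1−ICC)·r(within). At ICC 0.5:

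- between 0.6, within 0: 0.5 × 0.6 = 0.30
- between 0, within 0.6: 0.5 × 0.6 = 0.30

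The two situations cannot be told apart.

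**5. What the paired t-tests show.** Simulation with 25 completers:

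- Both measures fall by 0.8 SD of the change score and the changes are uncorrelated: both tests are significant in 94% of studies, with no individual tracking.
- Mean change is zero and the changes correlate 0.9: both tests are non-significant in 93% of studies, despite close tracking.

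**The case against.** The best reply is that section 9.1 states no explicit test of r. A test is implied only by section 9.2, which is sized per participant, and on that reading the 5% level holds. This stands: pooling is the most literal reading of section 9.1, not the only one. It does not rescue the clinical-evolution question, because one row per participant is purely between-person.

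A second reply is that the role for the primary objective is hedged, since section 9.1 only expects the approach to provide information. That is fair, but section 9.2 sends the clinical-evolution sample size to the same place and no other analysis is offered.

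Stronger readings that a reader might infer, and that the documents do not support:

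- **That 28 is too few.** It reproduces from its own inputs.
- **That the false-positive rate is 30% to 62%.** Those values rest on assumed ICCs and on pooling. Near ICC 0 there is almost no inflation.
- **That the paired t-tests are wrong.** They are valid for mean change.
- **That study day or monitoring length must be adjusted for.** Section 2.1 wants response to treatment compared with self-perceived improvement, so a decline shared by cough and VAS may be part of the signal. Inpatient length runs to discharge, so it is post-baseline and may depend on recovery.
- **That a change analysis is bound to be imprecise.** An observed r of 0.5 has a 95% CI of 0.13 to 0.75 with 25 people. But section 4.1 asks participants in general for VAS and LCQ, so more than 28 may contribute. With 200 (an assumption) the interval is 0.39 to 0.60.

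**Conclusion.** The point holds as a gap in the analysis specification, not as an arithmetic error. Three things can be read directly from the text: repeated days are not handled, the unit differs between sections, and no analysis links individual changes.

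The firmer harm is interpretive. A pooled r mixes two associations, a per-participant r shows only one of them, and the t-tests show neither. None of these answers whether Hyfe follows a patient's course. The inflated error rate is conditional: it needs the pooled reading and a non-trivial ICC in both measures. It ranges from none at ICC 0 to about 62% at ICC 0.7 with 30 days, and to about 33% with 7 days.

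This should be settled before analysis, because the clinical-evolution part of the primary objective has no other stated analysis.

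**What to change.** 1. Use one cough measure (coughs per recorded hour, as in section 7.2) and one unit of analysis in sections 4.1, 7.2 and 9.1.
2. If daily or weekly rows are analysed, fit a model with participant effects that splits cough rate into the participant mean and the within-participant deviation. Use participant-clustered standard errors or a participant-level bootstrap, and report both associations. Otherwise use one row per participant and label the result between-person.
3. Add a per-participant regression or correlation of change in VAS, and of change in LCQ, on change in cough rate, with 95% confidence intervals. Define start and end windows that do not overlap; two one-week windows would overlap in stays under 14 days.
4. State whether the average decline shared by cough and VAS counts as tracking. As sensitivity analyses, report the within-person association with and without study day, and change-on-change with and without monitoring length, noting that inpatient length is post-baseline.
5. In section 9.2, reconcile the primary-objective text with secondary objective 1. Say which analysis the 28 was calculated for, that 0.35 is f² with one row per participant, and that the 28 was not calculated for change-on-change.
6. Keep the paired t-tests as planned tests of mean change.

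The cost is wording in sections 4.1, 7.2, 9.1 and 9.2 and a little more analysis, with no new data or patients. The between-person p-value will usually be less favourable than the pooled one.
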